10.1.11 Visit 17 to Visit 18/M13 to M14

The following assessments should be done as listed in the study flow chart:

- AE/SAE will be monitored (if any).
- Concomitant medication (if any) will be checked at Visit 17 and Visit 18.
- Blood samples collection for hematology, ALT, serum creatinine, and urinalysis.
- Blood samples collection for lymphocyte phenotyping and for ADA at Visit 17 only.
- Blood samples collection for PK.

10.1.12 Visit 19/M15

The following assessments should be done as listed in the study flow chart:

- AE/SAE will be monitored (if any).
- Concomitant medication will be checked and reported (if any).

- Physical examination, including vital signs.
- Perform EDSS assessment.
- Blood samples collection for hematology, clinical chemistry laboratory assessments including thyroid function test and urinalysis.
- Blood samples collection for lymphocyte phenotyping and ADA.

10.1.13 Visit 20 to Visit 21/M16 to 17

The following assessments should be done as listed in the study flow chart:

- AE/SAE will be monitored (if any).
- Concomitant medication will be checked and reported (if any).
- Blood samples collection for hematology, ALT, serum creatinine, and urinalysis.

10.1.14 Visit 22/M18

The following assessments should be done as listed in the study flow chart:

- AE/SAE will be monitored (if any).
- Concomitant medication will be checked and reported (if any).
- Physical examination including vital signs.
- Blood samples collection for clinical laboratory assessments, clinical chemistry, thyroid function test, and urinalysis.
- Blood samples collection for lymphocyte phenotyping.
- Blood samples collection for immune markers (optional).
- Perform EDSS assessment.
- Perform SDMT and BVMT-R test.
- Recording of PedsQL/Ped NeuroQoL.

10.1.15 Visit 23 to Visit 24/M19 to M20

The following assessments should be done as listed in the study flow chart:

- AE/SAE will be monitored (if any).
- Concomitant medication will be checked and reported (if any).
- Blood samples collection for hematology, ALT, serum creatinine, and urinalysis.

10.1.16 Visit 25/M21

The following assessments should be done as listed in the study flow chart:

- AE/SAE will be monitored (if any).
- Concomitant medication will be checked and reported (if any).
- Physical examination including vital signs.
- Blood samples collection for clinical laboratory assessments including thyroid function test and urinalysis.
- Perform EDSS assessment.
- Blood samples collection for lymphocyte phenotyping.

10.1.17 Visit 26-Visit 27/M22-23

The following assessments should be done as listed in the study flow chart:

- AE/SAE will be monitored (if any).
- Concomitant medication will be checked and reported (if any).
- Blood samples collection for hematology, ALT, serum creatinine and urinalysis.

10.1.18 Visit 28/M24 EOTP

The following assessments should be done as listed in the study flow chart:

- AE/SAE will be monitored (if any).
- Concomitant medication will be checked and reported (if any).
- Physical examination including vital signs.
- Blood samples collection for clinical laboratory assessments including thyroid function test, ADA, and urinalysis.
- Blood samples collection for lymphocyte phenotyping.
- Blood samples collection for immune markers (optional).
- Perform Tanner staging.
- Perform MRI scan without contrast.
- Perform EDSS assessment.
- Perform SDMT and BVMT-R test.
- Recording of PedsQL/Ped NeuroQoL.

10.1.19 Safety monitoring phase Year 3 to Year 5

The following assessments should be done as listed in the study flow chart:

- AE/SAE will be monitored (if any).
- Perform EDSS assessment at every 6 months.

- Concomitant medication will be checked and reported (if any).
- Physical examination including vital signs at every 6 months.
- Blood sample collection for hematology, urinalysis, ALT, and serum creatinine every month.
- Perform clinical chemistry assessments including thyroid function test every 3 months.
- Perform MRI scan without contrast, PedsQL/Ped NeuroQoL, and cognitive tests yearly.
- Perform Tanner staging yearly.
- Blood samples collection for lymphocyte phenotyping and ADA yearly.

10.1.20 Relapse Visit

The following assessments should be done as listed in the study flow chart:

- Physical examination, including vital signs.
- AE/SAE will be recorded (if any).
- Perform EDSS assessment.
- Concomitant medication will be checked and reported (if any).

10.2 DEFINITION OF SOURCE DATA

Source data are defined as original documents, data, and records. This includes, but is not limited to the following: hospital records, clinic and office charts, study-specific source document worksheets including Neurostatus-EDSS worksheets, phone logs, memoranda, evaluation checklists, laboratory requisitions, and reports, MRI reports and images, local laboratory reports (if applicable), medication dispensing records, patient questionnaires, computer printouts, electronic data/information sources including IVRS/IWRS notifications, and any other documentation regarding the patient.

10.3 HANDLING OF PATIENT TEMPORARY OR PERMANENT TREATMENT DISCONTINUATION AND OF PATIENT STUDY DISCONTINUATION

During infusion courses, the IMP should be continued whenever possible. In case the IMP is stopped, it should be determined whether the stop can be made temporarily; permanent IMP discontinuation should be a last resort. Any IMP discontinuation must be fully documented in the electronic-Case Report Form (e-CRF). In any case, the patient should remain in the study as long as possible.

10.3.1 Temporary treatment discontinuation with investigational medicinal product(s)

Temporary treatment discontinuation may be considered by the Investigator because of suspected AEs. Reinitiation of treatment with the IMP will be done under close and appropriate clinical/and or laboratory monitoring once the Investigator will have considered according to his/her best

medical judgment that the responsibility of the IMP(s) in the occurrence of the concerned event was unlikely and if the selection criteria for the study are still met (refer to [Section 7.1](#) and [Section 7.2](#)).

For all temporary treatment discontinuations, duration must be recorded by the Investigator in the appropriate pages of the e-CRF.

10.3.2 Permanent treatment discontinuation with investigational medicinal product(s)

Permanent treatment discontinuation is any treatment discontinuation associated with the definitive decision from the Investigator or the patient not to re-expose the patient to the IMP at any time.

10.3.3 List of criteria for permanent treatment discontinuation

The patients may withdraw from treatment with the IMP if they decide to do so, at any time and irrespective of the reason, or this may be the Investigator's decision. All efforts should be made to document the reason(s) for treatment discontinuation and this should be documented in the e-CRF in the EOTP Visit.

Patients must discontinue the IMP for the following reasons:

- Pregnancy or intention for pregnancy.
- At patient/parents request (ie, withdrawal of the consent for treatment).
- If, in the Investigator's opinion, continuation with the administration of the IMP would be detrimental to the patient's well-being.
- Intercurrent condition that requires discontinuation of the IMP (eg, laboratory abnormalities, please refer to decision tree in [Appendix B](#)).
- Life threatening events (such as such as myocardial ischemia, pulmonary alveolar hemorrhage, HLH,...)
- At the specific request of the Sponsor.

Any abnormal laboratory value will be immediately repeated for confirmation (within 24 hours if possible), before making a decision of permanent discontinuation of the IMP for the concerned patient.

10.3.4 Handling of patients after permanent treatment discontinuation

Patients will be followed-up according to the study procedures specified in this protocol up to the scheduled date of study completion, or up to recovery or stabilization of any AE to be followed-up as specified in this protocol, whichever comes last.

All cases of permanent treatment discontinuation must be recorded by the Investigator in the appropriate pages of the e-CRF when considered as confirmed.

10.3.5 Procedure and consequence for patient withdrawal from study

The patients may withdraw from the study before study completion if they decide to do so, at any time and irrespective of the reason. Withdrawal of consent for treatment should be distinguished from withdrawal of consent for follow-up visits and from withdrawal of consent for nonpatient contact follow-up, eg, medical records check. Patients requesting withdrawal should be informed that withdrawal of consent for follow-up may jeopardize the public health value of the study.

If possible, the patients are assessed using the procedure normally planned for the end-of-study visit.

Patients who withdraw should be explicitly asked about the contribution of possible AEs to their decision to withdraw consent, and any AE information elicited must be documented. Preferably the patient should withdraw consent in writing and, if the patient or the patient's representative refuses or is physically unavailable, the site should document and sign the reason for the patient's failure to withdraw consent in writing.

All study withdrawals must be recorded by the Investigator in the appropriate screens of the e-CRF and in the patient's medical records when considered as confirmed. In the medical record, at least the date of the withdrawal and the reason should be documented.

For patients who fail to return to the site, unless the patient withdraws consent for follow-up, the Investigator must make the best effort to recontact the patient (eg, contact patient's family or private physician, review available registries or health care databases), and to determine his/her health status, including at least his/her vital status. Attempts to contact such patients must be documented in the patient's records (eg, times and dates of attempted telephone contact, receipt for sending a registered letter).

The statistical analysis plan (SAP) will specify how these patients lost to follow-up for their primary endpoints will be considered.

10.4 OBLIGATION OF THE INVESTIGATOR REGARDING SAFETY REPORTING

10.4.1 Definitions of adverse events

10.4.1.1 Adverse event

An AE is any untoward medical occurrence in a patient or clinical investigation patient administered a pharmaceutical product and which does not necessarily have to have a causal relationship with this treatment.

10.4.1.2 Serious adverse event

An SAE is any untoward medical occurrence that at any dose:

- Results in death, or,

- Is life-threatening, or,
Note: The term “life-threatening” in the definition of “serious” refers to an event in which the patient was at risk of death at the time of the event; it does not refer to an event which hypothetically might have caused death if it were more severe.
- Requires inpatient hospitalization or prolongation of existing hospitalization, or,
- Results in persistent or significant disability/incapacity, or,
- Is a congenital anomaly/birth defect.
- Is a medically important event.
Medical and scientific judgment must be exercised in deciding whether expedited reporting is appropriate in other situations, such as important medical events that may not be immediately life-threatening or result in death or hospitalization but may jeopardize the patient or may require medical or surgical intervention (ie, specific measures or corrective treatment) to prevent one of the other outcomes listed in the definition above.

Note: The following list of medically important events is intended to serve as a guideline for determining which condition has to be considered a medically important event. The list is not intended to be exhaustive:

- Intensive treatment in an emergency room or at home for:
 - Allergic bronchospasm,
 - Blood dyscrasias (ie, agranulocytosis, aplastic anemia, bone marrow aplasia, myelodysplasia, pancytopenia, etc),
 - Convulsions (seizures, epilepsy, epileptic fit, absence, etc).
- Development of drug dependence or drug abuse.
- ALT >3 x ULN + total bilirubin >2 x ULN or asymptomatic ALT increase >10 x ULN.
- Suicide attempt or any event suggestive of suicidality.
- Syncope, loss of consciousness (except if documented as a consequence of blood sampling).
- Bullous cutaneous eruptions.
- Cancers diagnosed during the study or aggravated during the study (only if judged unusual/significant by the Investigators in oncology studies).
- Chronic neurodegenerative diseases (newly diagnosed) or aggravated during the study (only if judged unusual/significant by the Investigators in studies assessing specifically the effect of a study drug on these diseases).
- Suspected transmission of an infectious agent: if any suspected transmission of an infectious agent via a medicinal product (eg, product contamination).

Hospitalization for the scheduled alemtuzumab infusions, not related with any AE, due to Investigator decision or local requirement, will not be considered as an SAE.

10.4.1.3 Adverse event of special interest

Any AESI will be reported to the Sponsor in the same timeframe as SAEs, ie, within 24 hours, as detailed in [Section 10.4.4](#).

An AESI is an AE (serious or nonserious) of scientific and medical concern specific to the Sponsor's product or program, for which ongoing monitoring and immediate notification by the Investigator to the Sponsor is required. Such events may require further investigation in order to characterize and understand them. Adverse events of special interest may be added, modified or removed during a study by protocol amendment.

The following AE will be considered as an AESI:

- Hypersensitivity or anaphylaxis.
- Pregnancy occurring in a female patient entered in the clinical trial. It will be qualified as an SAE only if it fulfills one of the seriousness criteria (see [Section 10.4.1.2](#)). Follow-up of the pregnancy in a female participant is mandatory until the outcome has been determined.
- Symptomatic overdose (serious or nonserious) with IMP/non-investigational medicinal product (NIMP).
 - An overdose (accidental or intentional) with the IMP is an event suspected by the Investigator or a nurse and defined as an increase of at least 30% of the dose to be administered in the specified duration or if the dose is administered in less than half the recommended duration of administration,
 - An overdose with the NIMP is an event suspected by the Investigator or spontaneously notified by the patient (not based on systematic pills count) and defined as at least twice the intended dose within the intended therapeutic interval, adjusted according to the tested drug,
 - Of note, asymptomatic overdose has to be reported as a standard AE.
- Increase in ALT (see the "Increase in ALT" flow diagram in [Appendix B](#) of the protocol).
- Other product specific AESI(s):
 - Autoimmune mediated conditions including but not limited to autoimmune encephalitis, cytopenias, ITP, autoimmune hepatitis, nephropathies including anti-glomerular basement membrane (GBM) disease, thyroid disorders and acquired Hemophilia A (see [Appendix B](#))
 - Temporally associated* pulmonary alveolar hemorrhage
 - Temporally associated* myocardial ischemia, myocardial infarction
 - Temporally associated* stroke
 - Temporally associated* cervicocephalic arterial dissection
(* Temporally associated: 1 to 3 days after the last infusion)
 - HLH,
 - Progressive multifocal leukoencephalopathy (PML)
 - Pneumonitis,
 - Serious infections including serious opportunistic infections (eg, Listeria infections, CMV, EBV), HPV associated with cervical dysplasia
 - Malignancy
 - Thrombotic thrombocytopenic purpura

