patients were nasopharyngitis, urinary tract infections (UTI), upper respiratory tract infections (uRTI), sinusitis, influenza, bronchitis, oral herpes and herpes zoster. Prophylactic acyclovir treatment was used effectively in the clinical studies to reduce risk of Herpes Simplex virus infection (HSV) and therefore patients should receive concomitant acyclovir starting on the first day of any alemtuzumab course and continuing for at least 1 month after the last day of the course. Preservation of innate immunity and relative sparing of memory lymphocytes, together with the preservation of serum immunoglobulins (14), may contribute to the relatively low rate of serious infections following alemtuzumab treatment in MS patients.

During the course of the clinical studies, malignancies were observed in both alemtuzumab- and IFNB-1a-treated patients. However, the annualized rates of malignancy were similar across all treatment groups, and moreover, the malignancy risk was similar to the background incidence in the general population. The risk of malignancy will be further investigated in a long-term observational study.

As previously mentioned, the identified risks of alemtuzumab in patients with RRMS include:

- IARs (including cerebrovascular, cardiovascular, and pulmonary alveolar hemorrhage events).
- Serious infections.
- Autoimmunity (notably, ITP, thyroid disorders, or rarely nephropathies and autoimmune hepatitis, and hepatic injury).

Alemtuzumab Post-Marketing Updates in Adult

In post-marketing pharmacovigilance (PV) monitoring, infrequent cases of temporally associated pulmonary alveolar haemorrhage, myocardial ischemia, stroke (including ischemic and hemorrhagic stroke) and cervicocephalic (eg, vertebral, carotid) arterial dissection have been reported. Reactions may occur following any of the infusions during the treatment course. In the majority of cases time to onset was within 1-3 days of alemtuzumab infusion. Patients should be informed about the signs and symptoms, and advised to seek immediate medical attention if any of these symptoms occur.

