9.3.1 Adverse events

Adverse events reported by the patient or observed by the Investigator will be monitored, and include:

- Occurrence, seriousness, grade/intensity, relationship to study drug, resolution, and outcome of serious adverse event (SAE), adverse event of special interest (AESI), and AEs.
- Assessment of IARs: An IAR is defined as any AE occurring during alemtuzumab infusion or within the 24 hour post-infusion period. However, some IARs may occur beyond 24 hours (such as pulmonary alveolar hemorrhage, stroke, cervicocephalic arterial dissection, myocardial ischemia, thrombocytopenia and myocardial infarction). Toxicity grade (severity) of IAR is based on CTCAE. The timing of IAR in relation to alemtuzumab administration and distribution of IARs based on toxicity grade (severity) observed in the study for both study periods will be assessed.

Refer to [Section 10.4.1](#) for details.

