The following infusion management procedures must be utilized for each infusion and each treatment course:

- Pre-infusion : Physicians should obtain a baseline ECG and vital signs (including heart rate and blood pressure measurement), screen for pre-existing hemorrhagic, cardiovascular (including venous thromboembolism) and cerebrovascular risk factors, screen for lung disease, review concomitant medications (eg, antiplatelet agents, anticoagulants), perform laboratory tests (complete blood count with differential, serum transaminases, serum creatinine, test of thyroid function and urinalysis with microscopy), and evaluate infusion-related risks. Physician should also apply the following contraindications when treating patients in this study:
 - Hypersensitivity to the active substance, or to any of the excipients
 - Human Immunodeficiency Virus (HIV) infection
 - Severe active infection
 - Uncontrolled hypertension
 - History of arterial dissection of the cervicocephalic arteries
 - History of stroke
 - History of angina pectoris or myocardial infarction
 - Known coagulopathy or on concomitant anti-coagulant therapy

It is at investigator's discretion to treat or not treat patient with alemtuzumab after clinical evaluation.

- During infusion: Continuous/frequent monitoring of heart rate, blood pressure assessment (at least hourly) and overall clinical status of the patients including consideration of the volume of fluids administered. The following are recommendations in case of clinical abnormalities/severe adverse event:
 - Interrupt infusion
 - Medically evaluate the patient guided by the adverse event profile of alemtuzumab prior to considering restarting therapy
 - Provide appropriate treatment as needed
 - Consider permanently discontinuing the alemtuzumab infusion if the patient shows clinical symptoms suggesting development of a serious adverse event associated with the infusion (myocardial ischemia, hemorrhagic stroke, cervico-cephalic arterial dissection or pulmonary alveolar hemorrhage).
 - Implement appropriate measures for patients at risk of venous thromboembolism: repeated ambulation during infusion and/or compression stockings.

- Post-infusion: Observation and education of patients
 - Observation for infusion reactions is recommended for a minimum of 2 hours after alemtuzumab infusion; 2 hours after infusion, patients should be cautious and reporting if any of the infusion reactions develop within 48 hours.

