11.4.1 Extent of study treatment exposure

Alemtuzumab will be administered by IV infusions in a supervised medical setting at a dose of:

- For patients ≥ 50 kg: 12 mg/day.
- For patients < 50 kg: 0.24 mg/kg/day.

There are two courses. The first treatment course includes 5 consecutive days of infusion, and the second treatment course is administered 12 months after the first treatment course and includes 3 consecutive days of infusion. The numbers and percentages of patients that received each possible level of total dose will be presented in the clinical study report.

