11.4.3 Analyses of safety data

11.4.3.1 Adverse events

AE observation period:

- Pretreatment AEs are defined as those AEs that developed or worsened prior to the 1st alemtuzumab dose.
- On treatment AEs are defined as those AEs that developed or worsened after the 1st alemtuzumab dose and until the end of the study (Month 60).
- Posttreatment AEs are defined as those AEs that developed or worsened after the ontreatment period.

On-study period will include pretreatment and ontreatment period. Treatment emergent adverse events (TEAEs) for analysis purpose will include all ontreatment AEs.

The primary analysis of adverse event reporting will be on TEAEs. Pretreatment AEs will be summarized separately.

The incidence of TEAEs (including IARs), AESI, will also be tabulated (frequencies and percentages) by severity, grade/intensity, and relationship to study drug. In tabulating severity of AEs on a per patient basis, the greatest severity will be assigned to a patient when there is more than one occurrence of the same AE with different reported severities. Relationships of the AE to treatment will be categorized as not related, or related. The highest level of association will be reported in patients with differing relationships for the same AE. Actions taken regarding treatment and patient outcome will also be listed.

In addition to IARs analysis above, TEAEs that occurs from start of infusion up to 72 hours postinfusion will be summarized if applicable.

The incidence of AEs leading to study discontinuations will also be summarized by treatment group, with details provided in the listing.

Death: The following deaths summaries will be generated:

- Number (%) of patients who died by study period (TEAE, on-study) and reasons for death summarized on the safety population.
- TEAE leading to death (death as an outcome on the AE e-CRF page as reported by the Investigator) by primary system organ class (SOC), high level group term (HLGT), high level term (HLT) and preferred term (PT) showing number (%) of patients sorted by internationally agreed order of SOC and alphabetic order of HLGT, HLT, and PT.

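### The AESI timing qualifier in 10.4.1.3 and Table 9 leaves out onset during an infusion or on an infusion day, although the protocol elsewhere expects these events then

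*Protocol*

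**What the plan says.** Section 10.4.1.3 lists pulmonary alveolar haemorrhage, myocardial ischaemia or infarction, stroke and cervicocephalic arterial dissection as product-specific AESIs. Each carries an asterisk leading to the definition "Temporally associated: 1 to 3 days after the last infusion". Table 9 in Section 10.4.6, which summarises the reporting rules, repeats that definition. AESI status applies to serious and non-serious events alike and triggers notification within 24 hours. Section 11.4.3.1 tabulates AESI incidence.

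Other sections describe the timing of the same events differently:

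- Section 4, on the post-marketing reports of these events: "Reactions may occur following any of the infusions during the treatment course". The next sentence reads "In the majority of cases time to onset was within 1-3 days of alemtuzumab infusion".
- Section 10.1.4, repeated in 10.1.10 for the second course, tells the site what to do while an infusion is running: "Consider permanently discontinuing the alemtuzumab infusion if the patient shows clinical symptoms suggesting development of a serious adverse event associated with the infusion". The parenthesis that follows names myocardial ischaemia, haemorrhagic stroke, arterial dissection and alveolar haemorrhage.
- Section 9.3.1: "An IAR is defined as any AE occurring during alemtuzumab infusion or within the 24 hour post-infusion period". It then lists these event types among the IARs that may begin later than 24 hours.
- Section 11.4.3.1 adds a supplementary summary: "TEAEs that occurs from start of infusion up to 72 hours postinfusion will be summarized if applicable".

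On the schedule, Section 11.4.1 states: "The first treatment course includes 5 consecutive days of infusion". The second course "includes 3 consecutive days of infusion".

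**The concern.** The qualifier differs from the rest of the protocol in two ways. Its anchor is the last infusion, where Section 4 speaks of any infusion. It also starts one day after that infusion, where Sections 9.3.1, 10.1.4, 10.1.10 and 11.4.3.1 all include the infusion itself. A stroke during the second infusion of course 1 is the kind of event for which 10.1.4 gives instructions, yet under the literal qualifier it is not an AESI.

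*Last* is not defined either, so two sites could classify the same event differently. At stake is whether the AESI tables contain the cases closest to exposure, and whether a non-serious case is notified within 24 hours.

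**Working it through.** No sample size or power figure is involved. The check counts days.

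**Inputs.** Infusions fall on Days 1-5 in course 1 and Days 1-3 in course 2 (Section 11.4.1). The qualifier runs from 1 to 3 days after the last infusion (Section 10.4.1.3, Table 9). As a reference span I take each infusion day plus the 3 days after it. This combines the any-infusion anchor of Section 4 with the start-of-infusion to 72-hour span of Section 11.4.3.1.

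**Reference span.** Course 1: 5 + 3 = 8 days (Days 1-8). Course 2: 3 + 3 = 6 days (Days 1-6).

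**Coverage under each reading, in calendar days:**

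| Reading | Course 1 | Course 2 |
|---|---|---|
| *Last* = final infusion of the course | Days 6-8: 3/8 = 38% | Days 4-6: 3/6 = 50% |
| *Last* = most recent infusion, every infusion day counted as day 0 | Days 6-8: 3/8 = 38% | Days 4-6: 3/6 = 50% |
| 1 to 3 days after any infusion (looser than the text) | Days 2-8: 7/8 = 88% | Days 2-6: 5/6 = 83% |

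The first two rows agree because infusions are daily: until the course ends, every day is itself an infusion day.

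**Where the reading matters.** Take an event on the morning of Day 2, before that day's infusion. If *last* means the infusion most recently given and dates are compared, the event is one day after the Day 1 infusion and qualifies. If any event on an infusion day is day 0, it does not. In elapsed hours it qualifies only if at least 24 hours have passed since the previous infusion. The between-infusion gap is therefore certain only if *last* means the final infusion of the course.

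**Where it does not matter.** An event during an infusion, or later that same day, is zero days after that infusion and fails both readings of *last*. Even the loosest row loses Day 1 of each course, because no earlier infusion in that course exists.

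**What still captures an event outside the window:**

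- If it is serious, it is an SAE under 10.4.1.2, and Table 9 gives it the same 24-hour deadline and the same AE and Safety Complementary forms.
- If it begins during an infusion or within 24 hours after it, it is an IAR under 9.3.1 and is tabulated as such in 11.4.3.1.
- If it begins within 72 hours after an infusion, it falls within the scope of the supplementary TEAE summary in 11.4.3.1.
- If it is non-serious and outside the qualifier, neither the AESI nor the SAE route requires notification within 24 hours.
- In none of these cases does it enter the AESI table.

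**The case against.** Sections 10.4.1.3 and Table 9 agree with each other, and the 1-3 day span evidently comes from Section 4, which gives the same span as the usual time to onset. A reader might infer that Section 4 sets a wider window. It does not: its span is the same and only its anchor differs. That stands. However, Section 4 describes a majority of cases, and the qualifier turns this into a hard boundary.

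The 72-hour summary is a supplementary table of all TEAEs, to be produced if applicable. Nothing obliges an AESI trigger to match it. That also stands, so it serves here as a model and not as a rule that has been broken.

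A reader might take 38% and 50% as the share of events captured. They are shares of calendar days, and they need a strict reading of *last*. The documents give no distribution of onset by day.

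A reader might also infer that AESI incidence will come out too low against adult data. The documents do not support that. They do not state the counting window behind the adult figures, and with the same window there would be no such bias. The AESI examples that Section 9.6 lists alongside the adult comparison are infusion-related reactions, autoimmunity and serious infections; these vascular events are not among them.

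Finally, most such events would be serious and so reported as SAEs. That stands and limits the consequence. It does not put the event into the AESI table.

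**Conclusion.** The qualifier is wrong as written, with limited consequences. Onset during an infusion, or later the same day, is literally outside under either meaning of *last*. Onset between infusions is also outside if *last* means the final infusion of the course; otherwise it depends on how days are counted. This conflicts with Sections 4, 9.3.1, 10.1.4 and 10.1.10, and with the window in 11.4.3.1.

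What is lost is AESI classification and tabulation, plus 24-hour notice of non-serious cases. There is no gap in SAE reporting, infusion-day events still enter the IAR analysis and the scope of the 72-hour summary, and no bias against adult data is shown. Section 4 calls these events infrequent, so few cases are likely. If about 50 patients are treated (the protocol's evaluable target, assumed here as the safety denominator), one case left out changes the tabulated incidence by 1/50 = 2 percentage points.

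The wording should be corrected because it omits the cases closest to exposure and lets sites classify the same event differently.

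**What to change.** Reconcile the sections above to one reporting definition and state it identically in 10.4.1.3 and in Table 9. It should be anchored to any infusion of either course, should include the infusion itself and the infusion day, and should say whether time is counted in hours or calendar days. The protocol's own span in 11.4.3.1, from the start of infusion to 72 hours after it, is an available model. This concerns reporting and tabulation only; no treatment or stopping instruction needs to change.

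The cost is one line in two places, made by protocol amendment as 10.4.1.3 provides for AESI changes, and possibly a few more AESI forms.
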